4.0 Study Design

4.1 Overall Design

This is a phase II, multi-center, double-blinded, placebo-controlled, randomized study aimed at comparing, two dosing frequencies of CYT107 and placebo in patients with sepsis. The study will be performed in parallel at multiple sites in the United States and France using identical study design and data collection. The results of the French and US investigative teams will be

combined for preliminary and final analysis. A REDCap database will be used for data management for all sites. A central computerized randomization center will be used to allocate treatments in both the US and French studies. *The current protocol deals with the United States investigative study.* For this preliminary trial of CYT107, there will be 4 investigative sites in the US, however, study enrollment is planned to take place at the coordinating site, Vanderbilt University Medical Center. If this current study demonstrates that CYT107 is safe and effective in increasing the ALC in septic patients, a larger trial of CYT107 will be conducted and additional sites in both countries may be recruited. The list of investigators and trial sites in the US are the following:

- [name] [name]; Professor of Anesthesiology, Vanderbilt University School of Medicine
- [name] MD; Professor of Anesthesiology, Medicine, and Surgery, Washington University School of Medicine
- [name] MD, Professor of Medicine, Ohio State School of Medicine
- [name] Ph.D., Professor of Surgery, University of Florida, Gainesville, School of Medicine.

4.2 Study Treatment

Up to thirty patients may be enrolled at 4 sites in the US, i.e., Vanderbilt, Ohio State, University of Florida, and Washington University School of Medicine, however, it is anticipated that the initial enrollment of 30 subjects will occur at Vanderbilt, Washington University and Limoges in France. (Note: the French sites may also enroll up to 30 patients such that a total of 30 evaluable patients will be available from the two countries). In the event that patient accrual is delayed in one country, all patients will be recruited from either the US or France alone. A computerized protocol will implement permuted block randomization in blocks of size three. This scheme ensures balance across the treatment groups for every third randomization. A maximum of 20 septic patients will be treated with CYT107 at a dose of 10µg/kg. There will be two dosing regimens as illustrated in Figure 8 (below). CYT107 will be administered intramuscularly at the dose of 10µg/kg (IBW), once or twice a week for a four week cycle. Ten septic patients will have CYT107 administered twice a week for 4 weeks. Ten septic patients will have two doses of CYT107 administered during the first week followed by one dose of CYT107 in conjunction with 1 dose of placebo for 3 additional weeks. Ten septic patients will receive placebo twice a week for four weeks along with routine standard of care per the clinical providers.

At approx. 48-120 hrs **after admission** for sepsis, those septic patients who meet the Inclusion/Exclusion criteria (see previous section) and provided written informed consent, will be entered into the study. The first dose of CYT107 (as indicated below) is at approx. 48-120 hrs after sepsis onset. The initial dose of study drug will be administered only in the ICU by the PI or research nurse. If patients have an INR greater than 2.5 or a platelet count less than 35,000, CYT107 will be administered by the subcutaneous route rather than by intra-muscular injection.

A staggered approach to CYT107 treatment will be used in which treatment will not be initiated in a newly enrolled patient until 24 hours after the previously enrolled patient has received the second dose of CYT107 without evidence of serious adverse event (SAE) occurrence.

In patients with coagulopathy (INR greater than 2.5 or a platelet count less than 35,000), CYT107 will be administrated subcutaneously.

Figure 8 Schematic study design of CYT107 Protocol

schematic "preliminary study" design																																																		
	Week 1							Week 2							Week 3							Week 4					Week 5				Week 6																			
days	1	2	3	4	5	6	7	8	9	10	11	12	13	14	15	16	17	18	19	20	21	22	23	24	25	...	28	29	...	35	36	...	42																	
IL-7	X			X				X			X				X			X				X			X																									
	X			X				X			P				X			P				X			P																									
PBO	P			P				P			P				P			P				P			P																									
ALC	X			X				X			X				X			X				X			X			X					X												X					
	TREATMENT																												FOLLOW UP																					
	IL-7 admin in 10 patients "high frequency dosing"																																																	
	IL-7 admin in 10 patients "low frequency dosing"																																																	
	10 Placebo Controls																					determination of ALC recovery and IL-7 clinical tolerance																												
	Absolute Lympho Counts																																																	

Dosing regimen for CYT107 in septic patients showed administration details of the “high frequency dosing” – (shown in red color) or the low frequency dosing (shown in blue color). The ALC is quantitated weekly throughout 6 weeks duration. Given that CYT107 will boost host immunity, we predict that patients treated with CYT107 will have decreased incidence of new secondary infection, decreased hospital readmissions (which generally are due to new secondary infections), and improved 60 day, 90 day, 180 days and one year mortality. Thus, these parameters will be recorded in all patients. The 60 day, 90 day, and one year data will be obtained by telephone interview, physician records, or by interrogating appropriate databases and newspaper obituary records. The patients will not have to be seen in clinic.

Additional experimental details:

- Patients with severe sepsis and organ failure who are admitted to the ICU are candidates. Septic patients who are not being treated in the ICU are not candidates for study enrollment.
- Septic patients will continue to receive the CYT107 to complete the full dose schedule even if their sepsis has resolved if they remain in the acute care hospital setting. Patients will not receive additional doses of CYT107 if they are discharged from the hospital.

If patients who are enrolled in the study fail to complete two weeks of the protocol for any reason such as death, discharge or transfer from the hospital, or study withdrawal decision by family or physician, then the patient will not be considered to have had an acceptable course of therapy with CYT107 to allow evaluation of its effects. The next patient to be recruited into the CYT107 study will be assigned the next randomization treatment until all groups have enrolled at least 10 subjects. In this manner, the investigators will be able to maintain proper patient

randomization to evaluate CYT107's efficacy. Note: research data for all subjects that underwent randomization and treatment will be completed regardless of length of time on study and will be entered into the database and reported to all Committees including the DSMB, FDA, IRB, etc.

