2.5 Risk-Benefit Ratio

Sepsis causes extensive apoptotic death of immune effector cells leading to an impaired immune system. CYT107 prevents sepsis induced cell death and improves survival in many clinically-relevant animal models of sepsis. We postulate that by improving host immunity, CYT107 will improve the ability of septic patients to eradicate their primary infection and decrease the incidence of new secondary infections. Given the low risk of adverse effects in patients treated with CYT107 and the potential for benefit, we believe that the risk benefit ratio lies greatly toward use of CYT107 in patients who have a highly likelihood of dying from sepsis; the expected mortality in septic patients who meet the entry criteria for this CYT107 study is approximately 45% at 60 days.

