6.2 Randomization

The randomization list will comprise three arms “CYT107 High frequency Arm” and “CYT107 Low frequency Arm”, and placebo Arm. A permuted-block randomization will be used in blocks of size of 3 and an allocation ratio of 1:1:1, stratified by study country (US and France). Subjects will be allocated randomly within each block. This procedure will be repeated until at

least 10 evaluable subjects are randomly assigned to each treatment group, totaling at least 30 evaluable subjects (between US and France).

Screening data, including lab results from screening and any relevant medical information, will be reviewed by the Research Nurse Coordinator and PI at each academic medical center for confirmation of all inclusion/exclusion criteria and randomization authorization.

After randomization authorization is granted by the PI at the responsible institution, the randomization assignment will be generated by computer. Each subject will be assigned the next available number. Subjects, investigators, and all study team members will be blinded to drug treatment. In the case of dropouts (either subject- or investigator-initiated), subjects will be replaced, to provide the required number of subjects. Randomization of replacements will be as follows:

1. Subjects withdrawn prior to randomization (prior to receiving CYT107 or placebo) will simply be replaced and the next subject will receive the same randomization assignment.
2. CYT107 treated subjects who are withdrawn after randomization while receiving the study drug treatments but prior to Day 14 will be replaced using with the next subject receiving the next randomization assignment. This will continue until a minimum of 10 patients have been randomized to each of the 3 cohorts and remained on study treatment through Day 13.
3. Subjects withdrawn or completing at least two weeks of study drug treatment will be considered evaluable and the following subject will receive the next scheduled randomization sequence.

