11.1 Patient Replacement Policy

For subjects that fail to reach the primary endpoint and for whom the dataset is considered as not evaluable (i.e. patients who have failed to complete at least two weeks of study drug treatment), the next randomization assignment will be assigned to the next patient to be enrolled on the study in order to reach a minimum of 10 evaluable subjects in all cohorts and the targeted sample size of 30 evaluable subjects overall..

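### Section 4.2's maximum of 20 CYT107-treated patients conflicts with replacement to 10 evaluable per arm: as a whole-study figure it holds only without early losses

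*Protocol*

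**What the plan says.** Protocol section 4.2 gives a ceiling on exposure: "A maximum of 20 septic patients will be treated with CYT107". It then describes ten patients in each of the high-frequency, low-frequency and placebo groups.

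Three sections provide for replacement:

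- Section 4.2 treats as not evaluable those who "fail to complete two weeks of the protocol for any reason such as death, discharge or transfer from the hospital", and the next recruit "will be assigned the next randomization treatment until all groups have enrolled at least 10 subjects".
- Section 6.2 continues "until a minimum of 10 patients have been randomized to each of the 3 cohorts and remained on study treatment through Day 13". It applies this to patients withdrawn after CYT107 treatment has begun. Allocation uses "blocks of size of 3 and an allocation ratio of 1:1:1", stratified by country.
- Section 11.1 gives the next assignment to the next patient "in order to reach a minimum of 10 evaluable subjects in all cohorts and the targeted sample size of 30 evaluable subjects overall".

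On enrolment, section 4.2 allows up to thirty patients at the US sites and adds that "the French sites may also enroll up to 30 patients such that a total of 30 evaluable patients will be available". It also allows all patients to come from one country if accrual lags in the other.

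On losses, the only rates given are late mortality. Expected mortality "is approximately 45% at 60 days" in section 2.5, and section 14.2 puts it at 40-45% at 60 to 90 days. The synopsis and section 4.2 end dosing at hospital discharge. No section gives a loss rate at Day 14.

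**The concern.** The ceiling counts patients treated, while the target counts patients evaluable. The two agree only if everyone dosed with CYT107 completes two weeks. A replaced patient has already been exposed, so each early loss in a CYT107 arm takes the treated number above 20.

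Section 2.4.3.2 says the product had not been tested in sepsis, so the number exposed is a basic figure in the plan. As written, a site that has treated 20 patients on CYT107 and has fewer than 10 evaluable in an arm cannot follow every section. Stopping breaches 6.2 and 11.1, and continuing breaches 4.2.

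**Working it through.** **1. Where 20 comes from.** Two CYT107 arms × 10 = 20. This is the number treated when the loss is zero.

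**2. The ceiling implied by enrolment.** 30 (US) + 30 (France) = 60. At 1:1:1, 60 × 2/3 = 40 on CYT107, twice the stated maximum.

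**3. Probability of no early CYT107 loss.** If each patient is non-evaluable with probability d, independently, the probability that all 20 are evaluable is (1 − d)^20. The value of d is an assumption throughout.

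**4. A value of d from document mortality.** Assume a constant hazard from 45% at 60 days. Mortality by Day 14 is then 1 − 0.55^(14/60) = 0.130. This counts deaths only; discharge, transfer and withdrawal would add to it.

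**5. Number treated.** A simple lower bound is 20/(1 − d), rounded up. It ignores the fact that a replacement takes the next assignment on the list and not the lost patient's arm. The scheme itself was simulated with one list in blocks of 3, stopping when every arm had 10 evaluable and with no enrolment ceiling.

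| d (assumed) | (1 − d)^20 | 20/(1 − d) | Mean CYT107-treated, simulated | Runs with at most 20 treated | Mean randomised |
|---|---|---|---|---|---|
| 5% | 36% | 22 | 21.8 | 25% | 32.8 |
| 10% | 12% | 23 | 23.6 | 5% | 35.4 |
| 13% (step 4) | 6% | 23 | 24.7 | 2% | 37.0 |
| 20% | 1% | 25 | 27.4 | 0.2% | 41.1 |
| 30% | 0.1% | 29 | 32.2 | none | 48.3 |
| 40% | <0.01% | 34 | 38.5 | none | 57.7 |

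If the last block is always completed, the expected number treated is twice the mean of the largest of three negative binomial counts: 24.1 at 10%, 25.2 at 13% and 39.1 at 40%.

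The share of runs within 20 is lower than (1 − d)^20 because a placebo loss opens a further block, which may assign CYT107 before it assigns placebo.

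**6. The enrolment ceiling.** At d = 40% about a third of simulated trials need more than 60 patients, and at 30% about 5% do. The mean of 38.5 therefore includes trials that section 4.2 would not allow.

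**7. Power if the 20 is enforced.** Section 9.1 claims more than 85% power with 10 per arm and response rates of 80%, 80% and 20%. Exact enumeration of the three-arm likelihood ratio test in section 9.2.3 (2 df, 0.05 level taken from the SAP) gives 86.0%, so the claim reproduces. With 20 treated, the expected evaluable number per CYT107 arm is 10(1 − d): 9 at 10% loss and 6 at 40%.

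| Evaluable per CYT107 arm | Power, placebo arm equally reduced | Power, placebo arm kept at 10 |
|---|---|---|
| 9 | 84.1% | 85.1% |
| 8 | 78.7% | 85.1% |
| 7 | 72.6% | 83.2% |
| 6 | 70.5% | 81.3% |

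**The case against.** **A US-only ceiling.** Section 4.1 says this protocol covers the US study, and section 4.2 allows up to 30 US patients. Thirty patients are ten complete blocks of three, which puts exactly 20 on CYT107 whatever the losses. On that reading the figure is correct. It does not fit its surroundings: the sentences that follow describe ten per arm for the study as a whole, and the same paragraph lets one country supply all the patients. In that case 30 enrolled yield 30 evaluable only with no loss.

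**Loose wording.** The 20 may have been meant as evaluable patients. The text says treated, and the same paragraph uses evaluable when it means that.

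**Unlimited exposure.** A reader might infer that replacement has no bound. It does: 30 per country, 60 in all.

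**The number treated.** A reader might infer that exposure will reach the high thirties. That needs a 40% two-week loss, which no document states, and it runs into the 60-patient ceiling. Document mortality alone supports only about 23 to 25.

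**Power.** A reader might infer that enforcing the 20 leaves the trial underpowered. Section 9.1 speaks of 10 subjects per arm and does not say evaluable. The SAP analyses everyone with at least one dose, so 10 treated per arm would all be included. A shortfall affects only the protocol's per-protocol (PP) and full analysis (FAS) datasets. The FAS in section 9.2.1.2 also requires all doses, so two-week replacement does not guarantee 10 per arm there anyway.

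**Safety oversight.** It does not depend on this figure: dosing is staggered, all treated patients are reported, and the DSMB reviews on an ongoing basis. That stands and limits the harm, but the contradiction remains.

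**Conclusion.** Section 4.2 contradicts the replacement rules in 4.2, 6.2 and 11.1, and its own enrolment allowance. As a whole-study figure, 20 treated is possible but requires no CYT107 loss before two weeks and no placebo loss that brings in further CYT107 assignments. To say that it cannot hold would go too far. At an assumed 10% loss it holds in about 5% of simulated trials, and at 20% in about 0.2%.

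The expected number treated is about 23 to 25 if only deaths count and the hazard is constant, and 23.6 to 38.5 for an assumed total loss of 10% to 40%. The upper end is partly cut off by the 60-patient ceiling. All of these figures rest on independent losses at an equal rate in every arm, and the simulated ones on a single list although the protocol stratifies by country.

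The effect on power is secondary. One patient fewer in each arm costs about 2 points (86.0% to 84.1%), and heavier loss costs more, but only in the PP and FAS analyses. The main consequence is a stated exposure that the plan's own rules would probably exceed.

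**What to change.** Reconcile the passages in section 4.2:

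1. Restate the 20 as evaluable CYT107 patients, 10 per arm, US and France combined.
2. Give the assumed Day-14 non-evaluable rate and the expected number treated that follows from it, as a range if the rate is uncertain.
3. Replace the maximum of 20 with the maximum CYT107 exposure implied by the existing ceilings, about 40 of 60 enrolled.

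This keeps the minimum of 10 evaluable per arm in 6.2 and 11.1. A rule that stopped enrolment with an arm below 10 would reverse those sections and is not needed to remove the contradiction.

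The change is to wording and to one stated assumption. Its cost is a less favourable exposure figure in the protocol.

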4.3 Endpoints

4.3.1 Primary Biological Activity & Safety Study Endpoints

- 1) *Weekly measures of absolute lymphocyte counts (ALC)* will be performed to determine the kinetics of restoration of ALC. Specifically, we will quantitate the increase of ALC at day 42 +/- 3 days, expressed as a percentage of baseline value determined at the time point that CYT107 was first administered (day 1). We will determine the number of patients who reach a 50% increase over the baseline value and we will also determine the percentage of patients reaching an ALC > 1200 at day 42 +/- 3 days in each group.
- 2) *Assessment of the clinical, biological, and immunological effects of CYT107* as well as its safety and tolerability, i.e., incidence and scoring of all adverse events: AEs and SAEs all over the study period, ending day 42 +/- 3 days, will be recorded and evaluated by the DSMB, Steering Committee, and secondary infections committee.

4.3.2 Secondary Biological Activity Study Endpoints

- 1) *PK Sessions*: Briefly each patient will be sampled on day 1 and day 22 at 0 (pre-dose), 1, 3, 5, 7, 9 and 24 hrs post CYT107 administration. Main PK parameters will be assessed including Model-independent PK analysis will be used to estimate Tmax, Cmax, half-life, clearance and area-under-the-curve (AUC).
- 2) *Pharmacodynamics effects on immune markers*: The investigative sites will also examine the effect of CYT107 to restore function of immune effector cells in patients with sepsis.
 - i. Effect of CYT107 to increase the percentage of patients reaching an ALC>1200 in each dosing group. (An ALC of 1200 represents the lower limit of normal for most hospital laboratories.)
 - ii. Effect of CYT107 on absolute numbers of CD4⁺T and CD8⁺T over the study period,
 - iii. Effects on circulating monocyte HLA-DR expression
 - iv. Effects on whole blood LPS-stimulated TNF- α
 - v. Assessment of CYT107 immunogenicity by detection and quantification of binding antibodies and detection of neutralizing antibodies in positive samples.
- 3) *Incidence and type of opportunistic secondary infections*: We will compare the effect of CYT107 to reduce hospital-acquired secondary infections in CYT107 septic patients versus a control group of septic patients who receive placebo. The rate of hospital-acquire secondary infections at day 42 is ~ 40%.(20) We postulate that CYT107 will reduce the rate of secondary infections by ~ 30-40%. We will also examine other clinical measures in the CYT107-treated septic patients and compare outcomes including: SOFA scores, ICU free days, hospital free days, ventilator free days, decrease

in readmissions to ICU for recurrent infections. We will also record at approx. 60, 90, 180 and 365 day (1 year) general health status and survival.

All end points will be evaluated in a global analysis, pooling the results of the US and French sites using REDCap as the common patient database. Results will be visible to all investigative centers.

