3.2 Secondary Objectives

3.2.1 To characterize CYT107 pharmacokinetics (PK) in this patient population

Another secondary objective of the study is to examine the pharmacokinetics (PK) and pharmacodynamics (PD) of CYT107 in patients with sepsis. Septic patients frequently have changes in circulating blood volume, impaired vasculature integrity with leakage of proteins into the interstitial space, and organ dysfunction. Although the investigators expect that CYT107's main PK parameters in septic patients will not be substantially affected by these alterations, it is important to define CYT107 AUC, C_{max} and half-life in this patient population. This information can be used to guide the proper dosing of CYT107 in a larger trial.

Up to now, CYT107 was administered by sub-cutaneous route to patients, but this route of administration is susceptible to increase the immunogenicity of the drug and patient's edema which is frequent in sepsis patients might alter the bioavailability. In this study the CYT107 product will be preferentially given by intra muscular administration. As exemplified for Interferon by Munafo et al(35), FSH by Steinkampf (36) et al., Alefacept by Sweetser (37) et al. and Onercept by Trincharde-Lugan (38) et al., the IM route is known to deliver pharmacokinetic profiles very similar to the S.C. route. Nevertheless the PK profile of CYT107 administered by I.M. will be determined during the study. Nevertheless, septic patients are susceptible to development of coagulopathy, which increases the risk of complications associated with

intramuscular drug administration. Thus, CYT107 will be administered via the subcutaneous route in coagulopathic (INR>2.5, platelet count less than 35,000/ul) patients.

3.2.2 To characterize CYT107 Pharmacodynamics - To determine if CYT107 can restore depressed functional activity of immune effector cells in patients with sepsis.

We will look at the ability of CYT107 to improve common markers of immune function that have been shown to correlate with outcome in patients with sepsis. Note that these tests are not standardized clinically available tests but rather tests that may be useful in the future to help guide administration of immunotherapeutic agents. These tests will be performed in the 3 investigators laboratories by their laboratory technicians.

- Effects to increase monocyte HLA-DR expression
- Effects to increase whole blood LPS-stimulated TNF- α

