6.4 Procedure for Days 60, 90, 180 and One Year Follow-up Period

Patients will be followed for 60, 90, 180 and 365 day outcomes regarding disposition, i.e., incidence of new secondary infections, long term status, i.e., still hospitalized, discharged to long term care facility or nursing home, discharged to home, and mortality.

Systematic blood sample for Immunogenicity testing at D60, repeated at day 180 and 360 if not negative for anti-CYT107 antibodies.

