7.2 CYT107 Pharmacokinetics

Pharmacokinetic profile will be determined in all patients.

Samples will be collected at D1 and D22 at pre-dose (0) and at approx:

1, 3, 5, 7, 9 and 24 hrs post dose

Samples will be analyzed for CYT107 content and data analyzed to determine the main PK parameters: C_{max}, T_{max}, AUC, half-life.

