8.7 BLINDING

8.7.1 Organization of Blinding

The study will be performed in a double-blind manner. The patient, the investigator and study center staff will be blinded to study drug allocation. The pharmacist will be unblinded to study drug and will prepare study treatment or placebo for a patient as specified by the randomization scheme.

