13.0 Collection and validation of data, and trial monitoring

13.1 Data Collection

Electronic Data Capture (EDC) will be used to collect individual data. An electronic Case Report Form (eCRF) is designed to contain information necessary for the evaluation of the patient and investigational agent. The eCRF must be completed in a timely manner following the visit and no more than a week after. The eCRF must be accurate and complete. All information required by the protocol is to be recorded in the eCRF based on source data. All REDCap data will be made available to the Sponsor in read-only format to review safety data and verify the validity and completeness of the forms.

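### Read literally, the data-access rules show patient-level CYT107 plasma results to centres and the sponsor before unblinding, which conflicts with the blinding sections

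*Protocol*

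**What the plan says.** **Blinding.** Protocol 8.7.1 states: "The patient, the investigator and study center staff will be blinded to study drug allocation". The synopsis adds care-providers and outcome assessors, and section 6.2 adds all study team members. Sections 8.7.3 and 9.3 lock the database and unblind when the last patient of the two national studies reaches day 60.

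**Access.** Section 4.3.2 ends its endpoint list with "All end points will be evaluated in a global analysis, pooling the results of the US and French sites using REDCap" as the shared database, and then: "Results will be visible to all investigative centers". Section 13.1 requires all protocol-required information in the eCRF, entered no more than a week after the visit, and adds: "All REDCap data will be made available to the Sponsor in read-only format to review safety data".

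**What the endpoints contain.** For pharmacokinetics, "each patient will be sampled on day 1 and day 22 at 0 (pre-dose), 1, 3, 5, 7, 9 and 24 hrs" after dosing (4.3.2), and "Pharmacokinetic profile will be determined in all patients" (7.2), so placebo patients are included. Section 4.3.2 also lists binding and neutralising antibodies, CD4 and CD8 counts, HLA-DR expression and stimulated TNF-α. Of the immune-function tests, section 3.2.2 says: "These tests will be performed in the 3 investigators laboratories by their laboratory technicians". Under section 6.4, antibody sampling at day 60 is "repeated at day 180 and 360 if not negative for anti-CYT107 antibodies".

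No section of the protocol limits, delays or masks these results before unblinding. The SAP says nothing about data access.

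**The concern.** The access rules and the blinding rules cannot both be followed as written. A CYT107 concentration curve around the first injection is close to a direct reading of whether the patient received CYT107. Lymphocyte counts come from routine care and cannot be hidden; the research assays can be.

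Three judgement-based processes are at stake:

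- **Causality grading.** A possible or probable relationship to study drug is part of the critical-event definition (12.1). A critical event is a listed reason for interrupting study drug (8.6.1), and causality also determines the related-event tables (9.2.5.1).
- **Investigator-initiated withdrawal before day 14.** This triggers replacement (6.2, 11.1) and affects who counts as evaluable in the per-protocol set (9.2.1.2). The SAP's set of all treated patients keeps the withdrawn patients but does not undo a selective withdrawal.
- **Detection of secondary infections.** Adjudication goes to a blinded panel (3.2.3, 10.3), but the panel can judge only what sites look for and report.

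The primary endpoint is a laboratory count and is less exposed.

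**Working it through.** **1. Is there a route to patient-level data before unblinding?** Put side by side: all endpoints go into REDCap (4.3.2); required data are entered within a week of the visit (13.1); results are visible to centres (4.3.2) and all REDCap data to the sponsor (13.1); unblinding waits for the last patient's day 60 (8.7.3). Followed literally, the answer is yes. Two links are not stated: when the assays are run and reported, and whether the 4.3.2 sentence means individual values or pooled results.

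**2. Is the sponsor meant to be blind?** Section 8.7.1 does not list it. Section 8.7.2 sends it a blinded alert after an emergency unblinding, which implies that it is.

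**3. How informative is each marker?** Allocation is 1:1:1 (6.2), so 2/3 of patients receive CYT107. Section 9.1 anticipates a rise of over 50% in ALC in more than 80% on CYT107 and less than 20% on placebo; 0.80 and 0.20 are used here.

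- Always guessing CYT107: 2/3 × 30 = 20 of 30 correct.
- ALC response, P(CYT107 | response) = (2/3 × 0.80) / (2/3 × 0.80 + 1/3 × 0.20) = 0.533 / 0.600 = 0.889.
- ALC response, P(placebo | no response) = (1/3 × 0.80) / (1/3 × 0.80 + 2/3 × 0.20) = 0.267 / 0.400 = 0.667.
- ALC response, overall accuracy = 2/3 × 0.80 + 1/3 × 0.80 = 0.80, or 24 of 30.
- Plasma profile: no assay performance is given. Assuming sensitivity = specificity = 0.90, 0.95 or 1.00, accuracy is the same figure: 27, 28.5 or 30 of 30.

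Section 2.3.1.1 reports raised endogenous IL-7 in lymphopenia, so the placebo background may not be zero. Each patient does have a pre-dose and six post-dose samples, so the signal is a rise within the patient. Both CYT107 arms receive active drug on days 1 and 22 (8.5), so these profiles cannot separate high from low frequency. T-cell counts are, like ALC, only probabilistic. Antibodies are probably insensitive, since section 2.3 expects low or no immunogenicity.

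**4. Could it reach allocation?** Blocks have size 3, stratified by country (6.2), each with two CYT107 and one placebo assignment. If earlier patients' status were readable in time and the block order known, the predictable patients per block would be two with placebo first, one with placebo second and one with placebo third. The mean is (2 + 1 + 1) / 3 = 1.33 of 3, or 44%. This is an upper bound under both conditions.

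**5. When does the antibody recall matter?** A new patient starts no sooner than 24 hours after the previous patient's second dose (4.2). That is 4 days after the previous patient's day 1. If the stagger is trial-wide, 30 patients need at least 29 × 4 = 116 days to enter, and unblinding comes at least 116 + 59 = 175 days after the first patient's day 1. Early patients' day-60 results therefore fall in the blinded period. A patient's day-180 visit precedes unblinding only if the last patient starts more than 180 − 60 = 120 days later, which takes slightly slower accrual or a few replacements. If the stagger runs per site, the overlap is shorter.

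**The case against.** The strongest reply is that the 4.3.2 sentence directly follows one about the pooled US and French analysis. In context it may mean only that both national teams will see the combined results, which exist after the day-60 lock. No section says that individual plasma or antibody values reach sites earlier, and the one-week eCRF rule gives no assay turnaround. This stands as a plausible reading. It would remove the risk from that sentence but not from 13.1, which covers all REDCap data and has no timing limit.

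A reader might infer that sites certainly can identify each patient's arm, and that plasma levels, antibodies and T-cell counts do so equally well. The documents do not support either. Early release of patient-level results is not stated, only serial plasma levels come near to identifying treatment, and even these do not give the dosing frequency.

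A reader might also infer that the antibody recall unblinds sites while it matters most. The result that triggers it comes from day 60, after that patient's last scheduled dose (day 25), day-42 endpoints and adverse-event recording to day 42 ± 3. Only later follow-up is exposed.

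Existing safeguards also count: the infection panel is blinded, and serious and critical events are reviewed separately by the sponsor and the DSMB (12.3, 12.5). They narrow the exposure. They do not cover what sites choose to investigate or whom they withdraw, and the sponsor's review is itself open to the same data.

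**Conclusion.** The point holds as a conflict between the access rules and the blinding rules, not as a demonstrated unblinding. Under the literal reading, centres and the sponsor would see a marker that sorts roughly 27 to 30 of 30 patients into CYT107 or placebo, compared with 24 from ALC response. That range rests on an assumed assay accuracy of 90 to 100% and on results being entered before unblinding. If the 4.3.2 sentence means pooled results after lock, the risk from it is nil and what remains is the sponsor access in 13.1. The change should be made because the text permits the harmful reading, the exposed outcomes are those that depend on judgement, and the correction is cheap.

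**What to change.** - **Section 4.3.2:** say that pooled results are shared with all centres only after unblinding. State that patient-level pharmacokinetic, anti-drug antibody and research immune-assay results (T-cell subsets, HLA-DR, stimulated cytokines) sit in a restricted REDCap group until then, hidden from site investigators, coordinators, adjudicators and the sponsor's trial team.
- **Section 13.1:** exclude those fields from the sponsor's view until unblinding.
- **Section 3.2.2:** have laboratory staff enter pharmacodynamic results by study ID without returning them to the clinical team.
- **Sections 6.4 and 7.3:** for patients whose day-180 visit falls before unblinding, either draw that sample from all of them, or accept and state that the recall reveals the antibody result. Sending a selective recall through the pharmacist or a laboratory would not mask it, because being recalled is itself the information.

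The cost is REDCap user-rights settings, a few sentences of protocol text and, under the first recall option, a few extra blood samples. Investigators wait until unblinding for research assays that are not used for care; section 3.2.2 itself describes the immune-function tests as not standardised for clinical use.
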